4.1 HoloLens application

4.1.1 Pre-operative phase

The patient will be screened for eligibility as mentioned above. Further screening assessments will include anamnesis, documentation of the medical history, clinical examination (including vital parameters) and baseline CT-imaging of the brain. If the patient is deemed eligible for inclusion, information on the trial will be provided to the patient. If the patient agrees to participate in the trial, a signed IC document will be obtained.

Upon inclusion, standard procedures for clinical management of patients requiring drain placement will apply. Baseline imaging of the brain is performed pre-operatively, as is common practice for these procedures. The obtained imaging material (as anonymized DICOM images) will be prepared for transfer to HoloLens (segmentation, 3D modelling and subsampling) using proprietary software developed by the SARA-consortium. Planning of the intervention itself will be performed either on a planning station (a computer equipped with the beforementioned software) or on the HoloLens itself, using the 3D models as guidance (see Part 10 for ethical considerations). This concludes all preparations required for the intra-operative application of the HoloLens.

4.1.2 Operative phase

The procedure itself will take place in a standardized fashion, performed by surgeons (in this case neurosurgeons or neurosurgeons in training) of different expertise levels (but always with adequate expertise and clearance to perform this procedure, as is current clinical practice). Surgical technique for the procedure is described below. The main difference is the use of the HoloLens as an AR device for visual aid during the procedure, which will not alter the operational workflow. The HoloLens will only be used immediately before and during the planned surgical procedures.

Surgical technique

The patient is installed on the operating table in the supine position. Patients will be sedated. The entry point is decided by the surgeon (usually at Kocher's point), based on the pathology at hand, pre-existing anatomical knowledge and knowledge of anatomical landmarks, but also surgical planning information based on the preoperative CT scan, as well as the augmented reality-displayed surgical trajectory. The entry point is then marked on the skin (after local shaving if necessary) and the patient undergoes standard surgical prepping (disinfection) and draping. A stab incision is made at the entry point, after which the hand drill is placed against the skull and a drill trajectory is made in the skull, following the predefined trajectory that the drain should follow. This trajectory is based, again, on the pathology at hand, pre-existing anatomical knowledge and knowledge of anatomical landmarks and trajectories, surgical planning information based on the preoperative CT scan, and, importantly, the augmented reality-displayed surgical trajectory. The drain is then placed through the drill hole and advanced until the predefined depth (decided upon based on the surgical planning). After placement, flow of CSF or blood (depending on the pathology) through the drain is checked, after which it is secured to the skin with suture thread and connected to a drainage system.

Analysis

The following measures pertaining to the surgical experience will be recorded during and after the surgical procedures:

- Duration of the surgical procedure (in minutes)
- Number of passes of the drain before correct placement
- Surgeon's estimate of success of placement (using the graded scale detailed below)
- Surgeon experience (detailed questionnaire available in Appendix B)

4.1.3 Post-operative phase & follow-up

Within 24h after surgery the patient will undergo a CT-scan to assess the position of the newly-placed drain. The primary endpoint, accuracy of drain placement evaluated on the immediate postoperative CT and graded according to clinical relevance, will be evaluated using the abovementioned Kakarla scale (*Table 2-1*).

In the further post-operative period, the patient's status will be monitored as it would be for every patient undergoing standard treatment for the abovementioned pathologies: in the immediate post-operative phase the patient is monitored in the Intensive Care Unit (ICU). In the following days the patient may undergo additional imaging of the brain if deemed necessary, and his/her clinical status will be continuously monitored, as is common practice. Based on the clinical evolution, the drain may or may not be removed, and the patient may or may not be transferred to the neurosurgical ward.

As soon as the patient is deemed adequately fit, he/she will be discharged from the hospital and a first follow-up appointment will be planned after 6 weeks. At this appointment the patient's clinical status and cranial imaging status will be assessed one final time, after which the patient has completed his/her participation in the trial.

4.2 Clinical evaluation, imaging & follow-up

Patients will be clinically monitored in accordance with standard of care for patients requiring EVD placement. We do not intend to do extensive research concerning the pathology, but rather want to get a notion of the possible difference in outcome related to the use of the HoloLens. The evaluations mentioned in this chapter will therefore be limited to the regular standard of care and only data obtained until the first follow-up appointment will be used for the trial. The schedule and types of assessments are presented in *Table 4*. The schedule is flexible as long as changes do not, in the opinion of the investigator, expose the patient to undue risk or induce bias in the evaluation of the endpoints. Data from the specified assessments will be collected in the **electronic Case Report Form (eCRF)**.

Protocol related procedures and assessments	Screening	Surgery	Post-operative period	Hospital discharge	Follow-up
	≤ Day 0	Day 0	Weekly		
Signed IC	X				
Prior medical history	X				
Physical examination	X	X	X	X	X
Clinical follow-up scales	X	X	X	X	X
Adverse events monitoring	X ↳			X	X
Concomitant therapy	X ↳			X	X
Other assessments					
CT-scan	X	X within 24h following surgery	(X) when deemed necessary for clinical reasons		X
Study treatment					
Surgery using HoloLens		X			
Survival status					X

Table 4. Protocol related procedures and assessments. The bold line indicates the end of the patient's participation in the trial.

Assessments outlined in *Table 4* include the following components:

- Prior medical history – diagnosis, prior and/or current treatments, history of other diseases (active or resolved), concomitant illnesses, and demographics.

- Physical examination – examination of major body systems (especially neurological evaluation), body weight and height (at screen only), vital parameters (i.e. temperature, blood pressure, and heart rate) and clinical follow-up scores (GCS, mRS, NIHSS, MGS; Appendix C).
- Adverse Events – Adverse events that are recorded in this trial are medical or surgical complications. Nature of the complication, date of appearance, relationship to the surgical procedure/trial intervention, offered treatment and outcome will be recorded. Patients will be followed for adverse events during the study until at least the first follow-up appointment, or until all serious adverse events have resolved or are determined to be “chronic” or “stable”, whichever is later. Serious adverse events should be monitored and reported from the time that the patient is included in the study (cfr. Part 8).
- Concomitant therapy – concomitant medications and treatments will be recorded from the time that the patient is included, during the study, and up until the first follow-up appointment.
- CT-scan – CT imaging of the brain:
 - Signs of increased intracranial pressure of any cause (e.g. trauma, anoxia, ...), requiring placement of an EVD (e.g. GCS \leq 8)
 - Hematoma volume and evolution, evolution of midline shift
- Survival status – information on the patient’s post-operative survival will be collected for all patients until the first follow-up appointment.

4.3 Concomitant therapy

The use of the HoloLens does not interfere with the patients’ (medicinal) therapy. Medical treatment will therefore be continued or adjusted based on the requirements for the planned surgical procedure. This includes the standard post-operative care and follow-up.

All concomitant medications and blood products, as well as interventions (e.g. analgesic use or paracentesis) received by patients until the end of study inclusion will be recorded on the eCRF.

4.4 Life Style Guidelines

The use of the HoloLens does not interfere with the patients’ life style. Lifestyle adjustments will therefore only be adjusted if necessary based on the requirements for the planned surgical procedure. This includes the standard period of post-operative care and follow-up.

5 Statistical design

This is a class II, single-arm, clinical pilot study investigating feasibility, safety and efficacy of a proprietary software solution for augmented reality-display, and registration and tracking of patient-specific anatomic models on the Microsoft HoloLens (further referenced to in this paragraph as “the experimental treatment”) in patients requiring EVD placement.

A patient is considered evaluable if he has signed informed consent and has undergone the HoloLens-assisted surgical intervention. Primary endpoint is accuracy according to the abovementioned Kakarla scale and can be evaluated within 24 hours after surgery. Patients will be encouraged to complete follow-up (which does not differ from standard follow-up for these pathologies) in order to evaluate the secondary endpoints (clinical outcome, cfr below) but will remain evaluable in the context of the trial even if planned follow-up has not been completed.

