5.1 Objective & endpoints

We wish to demonstrate the feasibility and added value of an AR based (neuro)navigation system implemented on the HoloLens for guidance during EVD placement. EVD placement accuracy will be assessed using the Kakarla scale, ranging from good (grade I) to poor (grade III) placement. These clinical outcome data will be compared to normal ranges based on historical values obtained from literature and from our institution.

Secondary endpoints:

- Improvement of user experience (intuitiveness, ergonomics, quickness; using the questionnaires in Appendix B).
- Decrease of duration of procedure compared to same procedure performed without AR (based on historical values of procedure time, recorded at our institution)
- Decrease of difference in outcome (accuracy scale) and of difference in duration of procedure between surgeons of different expertise levels compared to same intervention without AR (flattening of the learning curve)
- Improvement of clinical outcome measures with AR-assisted surgery compared to standard practice (using the scales in Appendix C)
- Improvement of pathology-specific clinical outcome measures:
 - Revision rate
 - Complication rate
 - Velocity of the decrease in ICP
 - Evolution of midline shift

Exploratory endpoints:

- Explore development and optimization of an efficient and ergonomic workflow in a well-structured pipeline (pipeline from imaging to display of holograms)
- Explore and describe necessity for continuous implementation of technical advances improving the AR experience, such as:
 - Correcting for inattentional blindness (confusion between real and virtual world),
 - Correcting for the use of historical images (i.e. updating preoperative images to better reflect the current situation),
 - Implementing marker-free navigational tracking,
 - Exploring cooperation by offering different points-of-view for multiple surgeons,
 - Explore assistance of these interventions by using telepresence,
 - ...

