5.4 Statistical analysis

Dichotomized comparisons will be used to compare drain placement accuracy performed with versus without surgical AR assistance. Results obtained from the Kakarla scale after surgery with the AR guidance will be tabulated and compared to historical values obtained from literature and from our institution. These historical values are based on previous research in drain placement (without the use of AR guidance), and will be matched with the cases of the current study.

To achieve these dichotomized comparisons, we will use cut-offs within the accuracy scale to define different benchmarks of good versus bad drain placement. The cut-off can be placed at either side of the 'suboptimal placement'-category (cfr. Part 1), depending on the degree of accuracy we wish to pursue: a comparison with the cut-off above this category will analyze the improvement of perfect placement, whereas the cut-off below this category will analyze acceptable drain placement in general. Given the eventual alternating hypothesis of increased placement accuracy related to the use of AR guidance, along with the small expected sample size, these comparisons will be performed through one-sided Fisher's exact tests.

6 Patient registration procedure

Prior to undergoing any study-specific procedure, patients must read the patient information brochure and sign the current **Institutional Review Board** (IRB)-approved IC form (see Part 10.3 for the procedure during emergency situations). Screening procedures can then take place as listed in Part 4. Subjects meeting the eligibility criteria for study participation will start experimental treatment as soon as is estimated possible by the investigator.

Patient withdrawal

A patient may withdraw from the trial at any time at their own request, or they may be withdrawn at any time at the discretion of the investigator or sponsor for safety, behavioral, or administrative reasons. Unless the subject specifically withdraws his consent for use of the obtained data, the patient will remain evaluable within the trial if he has undergone the AR-assisted surgical procedure since the primary endpoint and some secondary endpoints are based on results that are obtained immediately after the surgical intervention.

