If a subject does not return for the scheduled follow-up visit, every effort should however be made to contact the subject and to document subject outcome, if possible. If the subject withdraws consent, no further evaluations should be performed and no attempts should be made to collect additional data, and the data obtained until that point will not be used in the final analysis.

A patient may be withdrawn from the trial in case the surgical intervention cannot be performed for any reason (for example sudden unexpected adverse event preceding the surgery and precluding it), or in case of withdrawal of patient consent

7 Forms and procedures for collecting data

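### Feasibility is the stated purpose, but AR delivery is not measured, and a patient whose AR preparation fails before use can fall outside the evaluable set

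*Combined protocol and SAP*

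**What the plan says.** Section 5.2 gives feasibility for intraoperative use in critical care as the reason for stopping at 10-15 patients rather than 67. Section 5.1 opens with "We wish to demonstrate the feasibility and added value of an AR based (neuro)navigation system implemented on the HoloLens" and then measures this through Kakarla placement grade. The secondary endpoints are user experience, duration, learning curve and clinical outcomes. One exploratory endpoint reads "Explore development and optimization of an efficient and ergonomic workflow in a well-structured pipeline".

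The evaluable set is defined in section 5: "A patient is considered evaluable if he has signed informed consent and has undergone the HoloLens-assisted surgical intervention". Section 6, on withdrawal, repeats the condition: "the patient will remain evaluable within the trial if he has undergone the AR-assisted surgical procedure". Section 6 also says "A patient may be withdrawn from the trial in case the surgical intervention cannot be performed for any reason", which concerns the operation and not the AR system.

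Preparation of the AR model follows inclusion. Under section 4.1.1 the images "will be prepared for transfer to HoloLens (segmentation, 3D modelling and subsampling) using proprietary software". Section 4.1.2 introduces its list of operative measures with "The following measures pertaining to the surgical experience will be recorded during and after the surgical procedures". The four items are duration, number of passes, the surgeon's estimate of success and the surgeon questionnaire.

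Section 5.3 promises to account for every registered patient and to give the number not evaluable. Section 9.2 plans a post-hoc video review of whether the system worked properly.

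**The concern.** The product under test is software for display, registration and tracking. For a feasibility study of such a product, the basic result is how often the registered overlay could be obtained and used, and where it failed when it could not. No endpoint asks this, and no item in section 4.1.2 records it.

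The evaluability rule adds to the gap, because it is conditional on AR having been used. A patient who is included, whose segmentation or modelling then fails, and who has a conventional placement does not clearly meet it. That patient is among the most informative about feasibility. Section 5.2 says positive results may lead to a larger randomized trial. Its planners would want the delivery rate and the failing step, and this plan commits to neither.

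**Working it through.** **Text.** Setting the sections side by side:

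- Failure in preparation, device never used, drain placed conventionally. Sections 5 and 6 require an AR-assisted operation, so the patient can be left out. Section 6 does not name AR failure as a reason for withdrawal. The dropout rationale in section 5.2 covers only cancellation of surgery.
- Registration or tracking lost after the device is in use. The key term is undefined, so the patient may still be evaluable. The plan does not say.
- Reporting. Section 5.3 yields evaluable/registered, a crude proxy for delivery. It pools AR failure with deaths, consent problems and other causes, and requires no reason.
- Other sources. The pipeline endpoint (5.1), the video review (9.2) and the questionnaires (Appendix B) bear on technical performance but set no rate. A patient in whom the HoloLens was never used may have no HoloLens footage.

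**The plan's own figure.** The plan states no delivery or failure rate to reproduce. Its 67 in section 5.2 reproduces as 67 per group for a one-sided Fisher's exact test of 80% against 95% (power 0.806). This point does not depend on it.

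**Delivery proportion.** Inputs: n = 10 or 15 (section 5.2). Failure counts are assumptions: up to 4 of 15 and up to 3 of 10. The exact (Clopper-Pearson) 95% limits for x delivered of n are the 0.025 quantile of Beta(x, n-x+1) and the 0.975 quantile of Beta(x+1, n-x). When x = n the upper limit is 1.

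| Delivered | Proportion | Exact 95% CI |
|---|---|---|
| 15/15 | 100% | 78.2-100% |
| 14/15 | 93.3% | 68.1-99.8% |
| 11/15 | 73.3% | 44.9-92.2% |
| 10/10 | 100% | 69.2-100% |
| 9/10 | 90% | 55.5-99.7% |
| 7/10 | 70% | 34.8-93.3% |

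The chance of at least one failure is 1-(1-q)^n. At assumed q of 5%, 10% and 20% it is 40%, 65% and 89% for n = 10, and 54%, 79% and 96% for n = 15.

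**Effect on accuracy.** Let f be the number of failures, a the accuracy of AR-completed drains and p that of fallback drains. Grading every drain changes expected accuracy from a to ((n-f)a + fp)/n, a drop of f(a-p)/n, or f(a-p) drains. Inputs: p = 70-80% (null range, section 5.2; the 77-79% of section 1.3 lies inside it) and a = 95% (target, section 5.2) to 100%.

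- Smallest, either n: 1 × (0.95-0.80) = 0.15 drain, which is 1.0 point at n = 15 and 1.5 points at n = 10.
- Largest at n = 15: 4 × (1.00-0.70) = 1.2 drains, or 8.0 points.
- Largest at n = 10: 3 × (1.00-0.70) = 0.9 drain, or 9.0 points.
- If a = p the expected shift is zero. If p exceeds a, it reverses.

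These are expectations, not bounds. With four fallback drains, the chance that two or more are not well placed is 1 - p^4 - 4(1-p)p^3. At p = 0.80 this is 1 - 0.410 - 0.410 = 18%. At p = 0.70 it is 1 - 0.240 - 0.412 = 35%. If exactly two were not, and all 11 AR drains were good, 11/11 = 100% would become 13/15 = 86.7%, a shift of two drains.

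**The case against.** An as-treated accuracy set is an ordinary choice for a device pilot of 10-15 patients, and the protocol chose to express feasibility and added value through placement grade. Much of the wanted information may surface anyway: section 5.3 counts the non-evaluable, the pipeline endpoint would show segmentation problems, the video review looks at system function, and Appendix B asks about control of the system and need for support, with a free-text box. The failure counts above are assumed, and the wide intervals mainly reflect the small sample, which section 5.2 concedes.

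Most of this stands as mitigation. The as-treated analysis can stay, and technical performance is not unexamined. What remains is that none of these sources yields a delivery rate on a defined denominator with a stated reason for each failure.

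Two stronger readings are tempting. A reader might infer that patients with AR failure vanish from the report; section 5.3 contradicts that, since they would be counted among the non-evaluable. A reader might also infer that any registration or tracking failure excludes the patient. Section 4.1.2 has the device used immediately before and during surgery, so such a patient may have had AR-assisted surgery in the ordinary sense. Only failure before the device is used points clearly to exclusion.

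**Conclusion.** The point holds as a gap in endpoint and denominator definition. The plan does not commit to reporting how often the registered overlay was obtained and used, or why it was not, and its evaluability rule can set aside patients in whom AR failed before use. The trial is not invalid without the change; this is a cheap improvement.

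The delivery figures rest on assumed failure counts. A reader might infer that the accuracy result is inflated, or that the effect on it is negligible; the documents support neither. The expected shift is 0.15-1.2 drains at n = 15 and 0.15-0.9 at n = 10 if AR-completed drains do better than fallback drains by the margins assumed. It is zero if they do equally well, and the realised shift can be larger.

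**What to change.** 1. In section 5.1, add a feasibility endpoint. The denominator is all included patients planned for registered-overlay placement whose data may be used under section 10.3. The numerator is those in whom the overlay was obtained and used through drain insertion. Report it with an exact 95% CI and tabulate failures by step (preparation not started, segmentation, registration, tracking, other). Because section 10.3 allows inclusion before consent in emergencies and bars use of the data if consent is refused, state separately how many patients were lost for that reason.
2. In section 5, define what counts as HoloLens-assisted, including a failure part-way through.
3. Keep the accuracy analysis of AR-completed cases and add a sensitivity analysis grading every drain in the full set. The imaging is already planned: "Within 24h after surgery the patient will undergo a CT-scan to assess the position of the newly-placed drain". State in advance which analysis is primary; that choice is the sponsor's.

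The cost is wording in sections 5 and 5.1 and one eCRF item (overlay obtained and used through insertion, yes or no, with the failing step). No extra patients or scans are needed. The downside is one more item to complete and possibly less favourable reported results.
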